The primary aim of this study is to determine the energy intake-independent effects of leptin on energy metabolism in lipodystrophic subjects. Important aspects of energy metabolism to be studied include glucose metabolism, lipid metabolism, and energy expenditure. For each of these three aspects of energy metabolism, we will measure a primary, secondary, and one or more exploratory outcomes, as follows:

Glucose Metabolism

- **Primary outcome:** Total body insulin sensitivity (measured as glucose disposal rate during a hyperinsulinemic, euglycemic clamp)
- **Secondary outcomes:**
 - Hepatic insulin sensitivity (measured as suppression of endogenous glucose production during a hyperinsulinemic, euglycemic clamp)
 - Fasting plasma glucose
 - Fasting C-peptide
- **Exploratory outcomes:**
 - Insulin-like growth factor binding protein 2 (IGFBP2) and other novel mediators of leptin action on glycemia

Lipid Metabolism

- **Primary outcome:** Rate of lipolysis (measured using stable isotope tracers)
- **Secondary outcomes:**
 - Fasting plasma triglycerides
- **Exploratory outcomes:**
 - Rate of fatty acid turnover (measured using stable isotope tracers)
 - Liver triglyceride (measured using MRI and MRS)
 - Muscle triglyceride (measured using MRS)

Energy Expenditure

- **Primary outcome:** Total 24 hour energy expenditure (measured using indirect calorimetry in the metabolic chamber)
- **Secondary outcomes:**
 - Resting energy expenditure (measured using indirect calorimetry with a hood)

- Skeletal muscle work efficiency (measured as the exercise-induced incremental change in energy expenditure above resting energy expenditure)
- **Exploratory variables:**
 - Spontaneous physical activity (measure using portable accelerometers)
 - Thyroid function
 - Urine and plasma catecholamines
 - Cardiac autonomic nervous system tone (measured using heart rate variability analysis)

Additional outcomes include the following:

Thermal regulation

- Core versus peripheral body temperature
- Thermal comfort (measured using visual analog scales)

Endocrine

- LH pulsatility analysis

Other

- Blood pressure (measured using 24 hour ambulatory monitoring)
- Hunger and satiety (measured using visual analog scales)
- Markers of bone turnover (β -CTX and P1NP) will be measured to look for potential effects of leptin on bone formation and resorption.

Statistical Considerations

Sample Size Justification

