10. Glucose and Lipid Turnover: Stable isotope tracers will be used to measure glucose and lipid turnover. Endogenous glucose production will be measured using steady-state infusion of [6,6-²H₂] glucose tracer. The fractional rate of gluconeogenesis will be measured using steady-state oral dosing of deuterated water (²H₂O)⁴⁹. The rate of lipolysis will be measured using steady-state infusion of deuterium-labeled ²H₅-glycerol, and the fatty acid turnover rate will be measured using steady-state infusion of [U-¹³C₁₆] palmitate. Subjects will fast after 8 pm. A total of 3 grams per kg lean body mass of ²H₂O will be given in four divided doses every two hours at 9 pm, 11 pm, 1 am, and 3 am in order to enrich the subject’s body water pool to approximately 0.5% ²H₂O. Beginning at ~5 am, a primed [6,6-²H₂]glucose infusion will be given for 3 hours, after which blood samples to measure isotope enrichment will be measured over a period of 30 minutes at steady state. Two hours after the [6,6-²H₂]glucose infusion begins, a primed ²H₅-glycerol infusion, and unprimed [U-¹³C₁₆] palmitate infusion will be given for one hour, and

isotope enrichment will be measured over a period of 30 minutes at steady state. Tracer studies will be performed at the end of Period 1, in the middle and end of Period 2, and during the follow-up visit for subjects in the leptin-naïve group. To assess the effects of hyperinsulinemia on glucose turnover, the glucose tracer infusion will be continued during the euglycemic, hyperinsulinemic clamp study, below, with blood samples for tracer enrichment obtained during the steady-state period of the clamp.

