11. Euglycemic Hyperinsulinemic Clamp: This is the gold-standard test to measure insulin sensitivity. For insulin treated subjects, an overnight insulin drip may be given beginning at 6 pm the night prior to the clamp to maintain euglycemia. After an 8-hour fast, insulin will be infused at a dose of 120 mcU/m²*minute. This dose is designed to suppress endogenous glucose production and near-maximally stimulate glucose uptake in this group of very insulin resistant subjects. For a small number of subjects with extreme insulin resistance (requiring more than 200 units of insulin per day), higher doses of insulin may be used during the clamp study to create a state of hyperinsulinemia above the subject's baseline state. 20% dextrose enriched with 2.5% [6,6-²H₂] glucose tracer will be infused at a variable rate to maintain blood glucose at approximately 90 mg/dL. If subjects remain hyperglycemic without dextrose infusion after 1 hour of insulin infusion (by which time maximum insulin effect is expected), the clamp will be considered "failed" and will be prematurely terminated. During the insulin infusion, blood samples (0.5 mL) will be obtained every 5 minutes to measure blood glucose at the bedside. At steady state, the rate of dextrose infusion provides an estimate of insulin-stimulated glucose disposal. Additional samples will be drawn to measure the glucose and lipid tracers (described above), insulin, and other hormone levels. Due to the blood volumes and inconvenience of this test to participants, it will be performed once at the end of Period 1, once at the end of Period 2, and during the follow-up visit for subjects in the leptin-naïve group. If technical problems occur with a clamp study (e.g. IV failure or failure to attain steady-state glucose and insulin levels), the clamp may be repeated if blood volume limits permit.

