patients, blood draws will not exceed 5 mL/kg in a single day, or 9.5 mL/kg or 550 mL (whichever is smaller) per 8 week period. Patients may experience some discomfort at the site of the needle entry, and there is a risk of bruising at the site. There is a remote risk of fainting or local infection.

5. Oral Glucose Tolerance Test: Patients will be required to drink a very sweet glucose containing beverage. This may be associated with mild nausea or distaste. Due to serial blood draws, an intravenous line will be placed, with attendant risks of discomfort and possible skin infection.
6. Euglycemic Hyperinsulinemic Clamp Study: In order to assess insulin sensitivity, patients will receive an intravenous infusion of insulin and – via a second intravenous access – increasing amounts of glucose to maintain euglycemia. Insertion of the necessary intravenous lines may cause the above-mentioned discomfort and a possible skin infection. Insulin infusion can induce hypoglycemia and hypokalemia. Either event is very unlikely, since patients undergo frequent blood glucose measurements and are constantly observed for the presence of hypoglycemic symptoms by an experienced nurse and/or physician. However, in order to prevent complications, two patent, well-functioning intravenous lines are required during this procedure.
7. Glucose and Lipid Turnover: The stable isotopes C is not associated with any toxicity at the doses used in these studies ⁵³. Deuterium at the doses given may cause temporary dizziness. This risk will be minimized by dividing the ²H₂O dose into four aliquots, and by giving the doses at night while subjects lie in bed. If subjects need to get out of bed (e.g. to use the bathroom) the patient will first sit upright in bed for a few minutes prior to standing, and a nurse will be available to supervise and assist. Palmitate must be complexed to albumin prior to delivery, and thus carries the risks associated with use of human blood products. To minimize exposure to human albumin, uniformly labeled ¹³C₁₆ palmitate will be used, permitting use of the minimum possible dose of this tracer.
8. Resting Energy Expenditure: There are no significant risks associated with measurement of resting energy expenditure. Some patients may feel uncomfortable from lying still with a plastic hood over the head for approximately 30 minutes.

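### The clamp insulin rate is printed in micro-units (120 mcU/m²/min), about 1000 times too low for its stated purpose; the intended unit is most likely mU

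*Combined protocol and SAP*

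**What the plan says.** The clamp rate appears once, in Metabolic Testing item 11 (Euglycemic Hyperinsulinemic Clamp): "After an 8-hour fast, insulin will be infused at a dose of 120 mcU/m²*minute". The purpose follows directly: "This dose is designed to suppress endogenous glucose production and near-maximally stimulate glucose uptake in this group of very insulin resistant subjects".

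The same item adds two conditions. A clamp is stopped as failed if the subject is still hyperglycemic without dextrose "after 1 hour of insulin infusion (by which time maximum insulin effect is expected". For a few subjects with extreme insulin resistance, defined as "requiring more than 200 units of insulin per day), higher doses of insulin may be used during the clamp study", the aim is to raise insulin above the subject's own baseline.

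Two other sections rely on the clamp producing high insulin levels:

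- Outcome Measures makes it the source of the primary glucose outcome, "Total body insulin sensitivity (measured as glucose disposal rate during a hyperinsulinemic, euglycemic clamp", and of the secondary hepatic insulin sensitivity outcome.
- Metabolic Testing item 10 continues the glucose tracer through the clamp "To assess the effects of hyperinsulinemia on glucose turnover".

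Risks/Discomforts item 6 warns, "Insulin infusion can induce hypoglycemia and hypokalemia".

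**The concern.** The prefix mc denotes micro, so mcU is a millionth of a unit. A rate of 120 millionths of a unit per square metre per minute is negligible as an insulin infusion, yet the protocol expects it to drive glucose uptake close to its maximum in patients chosen for severe insulin resistance. The dose and its stated purpose cannot both be right.

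This is the operative dose for the procedure behind one of the three primary outcomes. Followed exactly, it would leave insulin essentially at the fasting level. The glucose disposal rate would then not be insulin-stimulated disposal, and suppression of endogenous glucose production by insulin would not be tested at all. A reader trying to reproduce the method from the protocol would also have the wrong rate.

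**Working it through.** The protocol gives no derivation of the rate, so there is no calculation of its own to reproduce. The check is unit arithmetic on the printed figure under each reading.

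**Inputs from the documents**
- Rate: 120 per m² per minute, unit printed as mcU (Metabolic Testing item 11).
- Time by which maximum effect is expected: 1 hour (same item).
- Threshold for allowing a higher clamp dose: more than 200 U/day (same item).
- Fasting insulin above 30 µU/mL, one of three alternative metabolic criteria (Inclusion Criteria, item 2c).

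**Assumptions, not in the documents**
- Body surface area of 1.4–2.0 m².
- Insulin clearance of 300–1000 mL/min/m².

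**Formulas**
- First-hour dose = rate × 60.
- Daily equivalent = rate × 1440.
- Rise in plasma insulin = rate ÷ clearance.

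| Quantity | As printed (mcU) | Read as mU |
|---|---|---|
| First hour, per m² | 120 × 10⁻⁶ × 60 = 0.0072 U | 120 × 10⁻³ × 60 = 7.2 U |
| First hour, per person (× 1.4 to 2.0) | 0.010–0.014 U | 10.1–14.4 U |
| Per day, per m² | 120 × 10⁻⁶ × 1440 = 0.173 U | 120 × 10⁻³ × 1440 = 172.8 U |
| Per day, per person (× 1.4 to 2.0) | 0.24–0.35 U | 242–346 U |
| Share of 200 U/day | 0.12–0.17% | 121–173% |
| Rise in plasma insulin | 0.12–0.40 µU/mL | 120–400 µU/mL |

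**Reading the results against the protocol**

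1. *Stated purpose.* About 0.01 U over an hour cannot nearly maximise glucose uptake in very insulin resistant subjects. A first-hour dose of 10–14 U is compatible with that aim.
2. *Hyperinsulinemia.* As printed, the rise is below 0.5 µU/mL, in a population where a fasting level above 30 µU/mL is itself an entry criterion. To raise insulin by even 30 µU/mL at the printed rate, clearance would have to be 120 ÷ 30 = 4 mL/min/m², far below the assumed range.
3. *The 200 U/day exception.* As printed, the infusion is less than 1% of this threshold, so subjects needing far less than 200 U/day would also not be raised above their baseline. Read as mU, it equals 200 U/day at a body surface of 200 ÷ 172.8 = 1.16 m² and exceeds it over the assumed range. This is supporting evidence only, because the protocol does not say the threshold was derived from the clamp rate, and a clamp is not run for a day.

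The two readings differ by exactly 1000. The assumed body surface and clearance ranges each span a factor of less than four, so they cannot close that gap.

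**Could it be a text-extraction fault?** This is unlikely. Micro-units elsewhere, for fasting insulin and for TSH, carry the Greek letter, whereas here the prefix is spelled out. The source PDF was not examined.

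**The case against.** The strongest opposing case is that this is an erratum.

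- **Recognisable.** Staff experienced with clamps would see the error, and it points towards too little insulin rather than too much. This stands.
- **Detectable.** Bedside glucose is checked every 5 minutes, and the 1-hour rule stops some failed clamps. That rule catches only subjects who remain hyperglycemic; those brought to euglycemia by an overnight insulin drip, or enrolled without diabetes, need not trigger it. The more general check is that insulin is measured during the clamp, and a clamp may be repeated if steady-state insulin is not reached. This also stands, and it makes an unnoticed failure improbable.
- **Weak support.** The risk statement is generic, and the same item calls those events very unlikely. The outcome and tracer sections only repeat that the clamp is hyperinsulinemic. Both points are fair. The finding rests on the conflict between the dose and the purpose stated in the next sentence, and needs neither.
- **Inferred replacement.** No section prints mU for this rate. That is correct: the documents show the printed unit to be untenable, but only the sponsor can confirm the intended value.
- **Reporting the infused rate goes beyond the slip.** It does. It is still worth doing, because the protocol allows unspecified higher doses in some subjects while the primary comparison is within subject between two clamps.

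These points limit the consequence. They do not reconcile the printed dose with its stated purpose.

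**Conclusion.** The concern holds. As printed, the clamp rate gives 0.0072 U/m² in the first hour and cannot produce the effect the protocol assigns to it. The likely intended rate of 120 mU/m²/min gives 7.2 U/m², a 1000-fold difference. That the printed unit is wrong does not depend on the assumed body surface or clearance. That mU was intended is an inference from the stated purpose, with weaker support from the 200 U/day exception.

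This should be fixed because it is the dose for a primary-outcome procedure. It does not change the sample size, power or alpha, and the documents give no indication that any clamp was run at the printed rate.

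**What to change.** Obtain the sponsor's confirmation of the intended rate, then amend Metabolic Testing item 11 to 120 mU/m²/min, or to whatever rate is confirmed. Report the insulin rate actually infused at each clamp, including any higher rate used for extreme insulin resistance, so that the comparison between the ends of Periods 1 and 2 can be interpreted.

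The cost is one corrected unit in an amendment and one reported variable that should already be in the clamp records. No procedure, sample or analysis is added. Appendix D (Waiver of Consent) mentions 28 patients already enrolled; for clamps already done the gain is mainly documentary, while any still to come would be run from a correct written dose.

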More detailed mechanistic studies of leptin's effects on glucose and lipid metabolism after 3-8 months have been performed on three patients with lipodystrophy (one acquired generalized and two congenital generalized)²⁵. Using stable isotope infusions in combination with the hyperinsulinemic, euglycemic clamp, these subjects in the leptin deficient state were shown to have elevated hepatic glucose production and severe hepatic insulin resistance compared to healthy controls. After leptin replacement for 3-8 months, hepatic insulin resistance decreased to nearly that of controls, and insulin-stimulated glucose disposal doubled. These changes were associated with an 86% reduction in hepatic triglyceride content and a 33% reduction in muscle triglyceride, suggesting that reduction in ectopic lipid may have contributed to the improvements in insulin sensitivity. Non-significant decreases in glycerol turnover were also observed following leptin treatment, suggesting that leptin increased lipolysis in any existing adipose tissue or within ectopic lipid stores. In a single subject, a 30% reduction in muscle fatty acyl CoA levels was observed after leptin replacement, offering support for the hypothesis that these compounds contribute to insulin resistance by interfering with insulin receptor substrate-1 (IRS-1) tyrosine phosphorylation, a key step in the insulin signaling cascade. In summary, leptin appears to improve plasma glucose and triglycerides within 1 week, while improvements in insulin sensitivity may be detectable by one month, with continued improvement thereafter, and changes in ectopic lipid storage may not be detectable for several months after leptin initiation.

The effect of leptin on lipid metabolism has also been examined in a randomized, controlled trial of leptin for 4 months in 17 men with HIV associated lipodystrophy³². In this trial, the authors did not find any effects of leptin treatment on lipid metabolism, including fasting triglycerides, rates of lipolysis, and fatty acid oxidation. This suggests that there may be differences in the effect of leptin on lipid metabolism in HIV patients versus the non-HIV infected population studied at NIH. These differences may be related to the severity of the phenotype (typically milder in HIV) or to the doses of leptin used in the HIV study (0.02-0.04 mg/kg/day, which is 25-50% of the lowest doses used in NIH studies).

Energy intake independent effects of leptin

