This is an exploratory study of the energy-intake independent effects of leptin initiation and withdrawal in lipodystrophy. Preliminary data are not available to generate estimates of power for each outcome to be tested. The primary comparisons to be tested for each outcome of interest are results at the end of Period 1 versus the end of Period 2, analyzed separately for each group of subjects (leptin-naïve versus leptin treated). Thus, sample size calculations are based on paired, before and after, comparisons within each group of subjects. The data and references used for power calculations are shown in the table, below. Data in the table using the 10% weight loss model are given as percent change from pre-weight loss values, while data from lipodystrophy patients are given as absolute differences between leptin treated and untreated states. All calculations assumed a sample size of 10 and an alpha of 0.05, without correction for multiple comparisons. Because the standard deviations (SDs) of differences between on and off leptin conditions were not reported in publications, the SDs of the difference (used to calculate power for paired comparisons) was estimated in two ways: First, the SDs of differences are calculated by assuming that the SDs of on and off leptin reported in the literature are independent (Power 1 in the table). Second, a “worst-case scenario” was assumed that the SDs on and off leptin in the literature are perfectly positively correlated (Power 2 in the table). The first scenario is the commonly used method, while the second case is the most conservative calculation.

Outcome	Model	Duration of leptin	Off-leptin mean (SD)	On-leptin mean (SD)	Power 1	Power 2
Total energy expenditure ¹¹ (% Δ in kcal/day)	10% wt loss	5 wk	-22% (15.8)	-6% (4.7)	0.92	0.79
Skeletal muscle work efficiency ¹¹ (% Δ in kcal/min expended during exercise vs. at rest)	10% wt loss	5 wk	20% (12.6)	3% (2.5)	0.99	0.97
Resting energy expenditure ²⁴	lipodystrophy	4 mo	35.5 (8.2)	33.6 (6.7)	0.14	0.11
T3 ¹¹ (% Δ)	10% wt loss	5 wk	-9% (6.3)	3% (3.2)	0.99	0.99

T3 ⁴³ (nmol/L)	lipodystrophy	4 mo	124 (37)	114 (26)	0.18	0.13
T4 ¹¹ (% Δ)	10% wt loss	5 wk	-7% (7.9)	-1% (1.3)	0.77	0.66
fT4 ⁴³ (pmol/L)	lipodystrophy	4 mo	1.05 (0.15)	1.03 (0.15)	0.09	0.08
TSH ⁴³ (μU/mL)	lipodystrophy	4 mo	1.37 (0.37)	1.24 (1.1)	0.10	0.09
Norepinephrine ¹¹ (% Δ)	10% wt loss	5 wk	-12% (15.8)	-7% (12.6)	0.19	0.14
Epinephrine ¹¹ (% Δ)	10% wt loss	5 wk	-40% (35)	28% (47)	0.98	0.83

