Sympathetic nervous system tone ¹¹ (% Δ in mean ECG R-R interval after atropine + esmolol vs. atropine alone)	10% wt loss	5 wk	-25% (22.1)	1% (1.6)	0.98	0.97
Liver volume ²⁴ (cm ³)	lipodystrophy	4 mo	3055 (1051)	2433 (763)	0.45	0.29
Total body insulin sensitivity ³¹ (glucose infusion rate during clamp, mg*kg ⁻¹ *min ⁻¹)	lipodystrophy	1 mo	2.5 (0.79)	3.7 (1.1)	0.87	0.63
Total body insulin sensitivity ²⁵ (glucose infusion rate during clamp, mg*kg ⁻¹ *min ⁻¹)	lipodystrophy	4 mo	1.2 (0.35)	5.4 (1.6)	1	1
Hepatic insulin sensitivity ²⁵ (% suppression of endogenous glucose production during clamp)	lipodystrophy	4 mo	40 (10.4)	82 (8.7)	1	1
Fasting glucose ³¹ (mg/dL)	lipodystrophy	7 d	172 (20)	120 (12)	1	0.99
Fasting triglycerides ³¹ (mg/dL)	lipodystrophy	7 d	700 (272)	260 (98)	0.99	0.98
Fasting triglycerides ³¹ (mg/dL)	lipodystrophy	14 d	700 (272)	110 (38)	1	0.99
Rate of lipolysis ²⁵ (glycerol turnover, μmol*kg fat mass ⁻¹ *min ⁻¹)	lipodystrophy	4 mo	78 (36)	25 (7)	0.99	0.99

Based on these calculations, a sample size of 10 subjects in each group (leptin-naïve and leptin-treated) will provide greater than 80% power (in most cases greater than 95%) for the following primary and secondary outcomes:

Glucose Metabolism

1. Total body insulin sensitivity
2. Hepatic insulin sensitivity
3. Fasting plasma glucose

Lipid Metabolism

1. Rate of lipolysis
2. Fasting triglycerides

Energy Expenditure

1. Total energy expenditure
2. Skeletal muscle work efficiency

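### The primary glucose outcome is defined as glucose disposal, but the only derivation given is the dextrose infusion rate, which also moves with hepatic glucose output

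*Combined protocol and SAP*

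**What the plan says.** Outcome Measures, under Glucose Metabolism, names the primary outcome as "Total body insulin sensitivity (measured as glucose disposal rate during a hyperinsulinemic, euglycemic clamp". A secondary outcome from the same clamp is "Hepatic insulin sensitivity (measured as suppression of endogenous glucose production during a hyperinsulinemic, euglycemic clamp".

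Metabolic Testing, item 11 (Euglycemic Hyperinsulinemic Clamp), says that at steady state "the rate of dextrose infusion provides an estimate of insulin-stimulated glucose disposal". No other section gives a way to derive the primary variable. Analysis of Primary Outcomes names the tests (paired t or Wilcoxon, then mixed models) but not the derivation. It also plans to correlate change in total body insulin sensitivity with change in hepatic insulin sensitivity.

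In the power table under Sample Size Justification, both rows for this outcome are labelled "glucose infusion rate during clamp". The text below the table then lists total body insulin sensitivity among the outcomes with more than 80% power.

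The protocol does collect what disposal needs. Item 10 (Glucose and Lipid Turnover) says that "the glucose tracer infusion will be continued during the euglycemic, hyperinsulinemic clamp study", with enrichment samples at clamp steady state, and item 11 adds glucose tracer to the infused dextrose.

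**The concern.** Infusion rate and disposal are the same number only when the liver's glucose output is fully suppressed. Otherwise infusion rate falls short of disposal by the residual EGP. A shortfall that was the same on and off leptin would cancel in a paired comparison. Here the plan itself expects it to change with leptin, and the Introduction names lower hepatic gluconeogenesis as a major leptin effect.

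If the primary outcome were analysed from uncorrected infusion rate, three things would follow:

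- Part of a hepatic effect would be reported as a change in disposal: a gain in the leptin-naïve group, a loss in the withdrawal group.
- The primary and the hepatic secondary outcome would overlap, because residual EGP enters both.
- For the same reason, part of the planned correlation between them would be built in.

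The stated power would also refer to a quantity other than the defined outcome.

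**Working it through.** **Inputs (power table unless noted; rates in mg/kg/min)**

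- Infusion rate, 1-month study (reference 31): 2.5 (SD 0.79) off leptin, 3.7 (1.1) on.
- Infusion rate, 4-month row (reference 25): 1.2 (0.35) off, 5.4 (1.6) on.
- EGP suppression, reference 25: 40% off, 82% on.
- Disposal, reference 25, from the Introduction (Leptin in lipodystrophy): "hepatic insulin resistance decreased to nearly that of controls, and insulin-stimulated glucose disposal doubled".
- Basal EGP: not given in the documents.

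**1. Reproduce the stated power (1-month row: 0.87 and 0.63).** The plan states that "All calculations assumed a sample size of 10 and an alpha of 0.05, without correction for multiple comparisons". Power 1 is obtained by "assuming that the SDs of on and off leptin reported in the literature are independent".

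- SD of the difference = √(0.79² + 1.1²) = 1.354. Power = Φ(1.2 × √10 / 1.354 − 1.645) = 0.876, against 0.87 stated.
- With the SD taken as the sum, 0.79 + 1.1 = 1.89: Φ(1.2 × √10 / 1.89 − 1.645) = 0.642, against 0.63 stated.

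Both agree to within about 0.01, on a one-sided normal approximation. Sidedness is not stated, and summing the SDs corresponds to perfect negative rather than positive correlation; those are separate matters. What counts here is that the input is infusion rate.

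**2. The identity.** At steady state, with urinary loss taken as nil:

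infusion rate = disposal − residual EGP, where residual EGP = (1 − suppression) × basal EGP.

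So change in infusion rate = change in disposal + fall in residual EGP.

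**3. The same-source check (reference 25).** Infusion rate rises 5.4 / 1.2 = 4.5-fold, while disposal doubles. Let E be basal EGP, assumed equal on and off leptin.

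- Disposal off = 1.2 + 0.60E; disposal on = 5.4 + 0.18E.
- Exact doubling: 5.4 + 0.18E = 2 × (1.2 + 0.60E), so 3.0 = 1.02E and E = 2.94.
- Disposal is then 2.96 off and 5.93 on, a change of 2.96.
- Fall in residual EGP = 0.42 × 2.94 = 1.24. Share of the 4.2 change in infusion rate = 1.24 / 4.2 = 29%.

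**4. Sensitivity.** Let disposal rise r-fold and basal EGP on leptin be k times its off-leptin value. Then E = (5.4 − 1.2r) / (0.60r − 0.18k), and the hepatic part is (0.60 − 0.18k) × E.

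| r | k | E | Hepatic part | Share of 4.2 |
|---|---|---|---|---|
| 1.8 | 1 | 3.60 | 1.51 | 36% |
| 1.8 | 0.5 | 3.27 | 1.67 | 40% |
| 2.0 | 1 | 2.94 | 1.24 | 29% |
| 2.0 | 0.5 | 2.70 | 1.38 | 33% |
| 2.2 | 1 | 2.42 | 1.02 | 24% |
| 2.2 | 0.5 | 2.24 | 1.14 | 27% |

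**The case against.** The strongest reply is that this is an unstated formula rather than a wrong method. Outcome Measures says disposal. Item 11 says only that infusion rate estimates it, and does not name the analysis variable. Tracer sampling in the clamp shows that the team can compute disposal. This stands in part: a reader might infer that the protocol has chosen uncorrected infusion rate for the primary analysis, and no section says so. But the only derivation on the page is infusion rate, and a better one is available from data already planned, so more than a missing detail is at issue.

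The second reply concerns transfer. The clamp insulin dose was chosen with suppression of EGP in mind, and may be raised in extreme resistance. The 40% and 82% figures come from three patients with generalized lipodystrophy after 3-8 months, at a clamp dose the documents do not give. This trial takes all subtypes and measures at 14 days. That stands, and the share here may be smaller. It does not remove the point: item 11 describes these subjects as very insulin resistant, and suppression is itself an outcome expected to vary.

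Two stronger readings are tempting. One applies the 40% and 82% figures to the 1-month infusion-rate change of 1.2 and concludes that most or all of that change is hepatic. That joins suppression from one study to infusion rates from another; the documents give neither suppression nor disposal for the 1-month study, so neither that conclusion nor a revised power for that row follows. The other is that a purely hepatic effect is the likely explanation. The only source with both figures reports that disposal itself doubled.

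**Conclusion.** The concern holds as a mismatch between the defined primary outcome and the only derivation given for it. In the one cited study where both can be compared, about 29% of the change in infusion rate is hepatic, with a range of 24-40%. That estimate assumes steady state, no urinary glucose loss, disposal and infusion rate in the same units, group means that can be combined, and doubling between 1.8- and 2.2-fold with basal EGP on leptin unchanged or halved. It illustrates that the gap can be material; it does not forecast the bias in this trial, which arises only if infusion rate is analysed uncorrected and EGP is incompletely suppressed.

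What is at risk is attribution to disposal, the separation of the primary from the hepatic secondary outcome, and the correlation between them. The broad null of no leptin effect on energy metabolism remains testable. Nor is the power claim shown to be false: it was calculated for infusion rate and has not been shown for disposal. In the 4-month row, a disposal change of 2.96 with the infusion-rate SD of √(0.35² + 1.6²) = 1.638 carried over (an assumption) would still give power near 1, since Φ(2.96 × √10 / 1.638 − 1.645) exceeds 0.99. The protocol should be changed, and the change is small.

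**What to change.** 1. In Outcome Measures and in item 11, state that the primary glucose outcome is tracer-derived glucose disposal at clamp steady state, that is, infusion rate plus tracer-measured residual EGP. Name the uncorrected infusion rate as a sensitivity measure.
2. In Sample Size Justification, add that power for this outcome was calculated for infusion rate and is not shown for disposal. The table rows already carry the right label and need no change.

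The cost is wording. The labelled dextrose, the continued tracer infusion and the steady-state samples are already planned, and residual EGP must be computed anyway for the hepatic secondary outcome. A term for urinary glucose loss is not requested, because the 24-hour urine collections are tied to the metabolic chamber stays and none is planned during the clamp.

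One limit remains. Disposal and EGP suppression would share tracer measurement error, so the planned correlation between them should still be read with care.
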